6.12.1 Adverse Events

Adverse events (AEs) will be classified as pre-treatment adverse event, treatment-emergent adverse event (TEAE) and post-treatment adverse event. Pre-treatment AE is defined as the AE occurring prior to the start of the deflazacort treatment.

TEAE is defined as the AE occurring or worsening on or after the first deflazacort dose and up to 30 days after the last deflazacort dose. Post-treatment AE is defined as the AE occurring after 30 days of the last deflazacort dose.

If a subject experience the same preferred term multiple times, the event will be counted only once and by the greatest severity.

TEAEs will be summarized by System Organ Class (SOC) and Preferred Term (PT) according to the Medical Dictionary for Regulatory Activities (MedDRA, version 23.1).

A treatment-related AE is defined as an AE as being possibly or probably related to the study drug. If an AE has a missing relationship it is assumed to be related to the study drug for analysis purposes.

An overall TEAE summary table will be provided with following information:

- The number of subjects with at least one TEAE
- The number of subjects with at least one treatment related TEAE
- The number of subjects with at least one Grade 3 or Grade 4 TEAE
- The number of subjects with a Grade 5 TEAE (Fatal)
- The number of subjects with at least one SAE
- The number of subjects with at least one TEAE leading to treatment discontinuation

QMD Ref: Worldwide-TMP-ST-005-7.0 Effective: 12Aug2019	Governing QMD: Worldwide-SOP-ST-001
Confidentiality Statement	
This document is the property of Worldwide Clinical Trials Inc. and may not be duplicated, copied, altered or removed from company without prior approval from Worldwide Quality Assurance or in compliance with Worldwide Standard Operating Procedures.	

Worldwide Clinical Trials Controlled Quality Management Document		
 WORLDWIDE CLINICAL TRIALS	Sponsor:	PTC Therapeutics, Inc
	Protocol Number:	PTCEMF-GD-004
STATISTICAL ANALYSIS PLAN		

- The number of subjects with at least one TEAE leading to dose reduction or interruption

In addition, the All TEAE by SOC and PT summary tables will be provided.

Detailed listings by subject of all AEs (pre-treatment AEs, TEAEs, related TEAEs, serious TEAEs, TEAEs leading to early termination of the study and TEAEs leading to death) will be provided. In addition, listings of SAE, treatment related TEAE, TEAE leading to treatment discontinuation, TEAE leading to dose reduction/interruption, and Grade 3/4/5 TEAEs will be provided as well.

6.12.2 Laboratory Data

Listings of clinical laboratory data with abnormal flags will be provided by subject, visit, and laboratory parameters. In addition, clinically significant laboratory measurements recorded throughout the study and serum pregnancy results will also be presented in the by subject listing.

6.12.3 Vital Signs

Assessments of vital signs including height, weight, BMI, diastolic blood pressure, pulse rate and systolic blood pressure will be presented in the by-subject listings only.

6.12.4 Electrocardiogram Data

ECG parameter results including overall interpretation, heart rate, PR interval, QRS duration, QT interval, QTcB interval, QTcF interval and RR interval will be presented in the by-subject listings only.

6.12.5 Physical Examination

Physical examination results will be presented in the by-subject listing only.

6.12.6 Ophthalmology Examination

Ophthalmology Examination results will be presented in the by-subject listings only.

6.12.7 Bone Density

Bone density as assessed by dual-energy X-ray absorptiometry (DEXA) will be summarized with raw scores and normalized scores for total hip bone mineral density (BMD), total body BMD and lumbar spine BMD. The normalized scores will be calculated based on Third United States National Health and Nutrition Examination Survey (NHANES III³) data and adjusted by gender.

QMD Ref: Worldwide-TMP-ST-005-7.0 Effective: 12Aug2019	Governing QMD: Worldwide-SOP-ST-001
Confidentiality Statement	
This document is the property of Worldwide Clinical Trials Inc. and may not be duplicated, copied, altered or removed from company without prior approval from Worldwide Quality Assurance or in compliance with Worldwide Standard Operating Procedures.	

Worldwide Clinical Trials Controlled Quality Management Document		
 WORLDWIDE CLINICAL TRIALS	Sponsor:	PTC Therapeutics, Inc
	Protocol Number:	PTCEMF-GD-004
STATISTICAL ANALYSIS PLAN		

First, the means and the standard deviations (SDs) will be calculated for each gender using NHANES III DEXA data as the reference means and SDs. Then the normalized z-score² will be derived using the following formula:

$$\text{Normalized score} = \frac{\text{Measured BMD} - \text{Mean BMD of gender matched reference group}}{\text{SD of gender matched reference group}}$$

Raw scores, normalized scores, and change from baseline in raw scores and normalized scores will be summarized by analysis visits.

Since not all subjects will have DEXA or X-ray assessed due to the availability or the local ethical regulation, the summary tables of DEXA or X-ray will be based on the Safety Population who had performed the assessments.

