## 4 STUDY POPULATION

The target population for this study is subjects,  $\geq 18$  years of age with LGMD2I.

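### The BMD z-score in SAP 6.12.7 is standardised by gender only, with no age matching and no stated reference ages, so its levels mix age with bone status (minor)

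*SAP*

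**What the plan says.** SAP 6.12.7 summarises DEXA results as raw scores and as "normalized scores for total hip bone mineral density (BMD), total body BMD and lumbar spine BMD". The normalised scores are based on NHANES III "data and adjusted by gender".

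The derivation has two steps. In the first, one mean and one SD "will be calculated for each gender using NHANES III DEXA data as the reference means and SDs". The second step is introduced with the words "Then the normalized z-score² will be derived using the following formula" and takes the measured value minus the "Mean BMD of gender matched reference group", divided by the SD of the same group. Age appears in neither step, and no age range is given for the reference sample.

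On reporting: "Raw scores, normalized scores, and change from baseline in raw scores and normalized scores will be summarized by analysis visits".

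The target population in Protocol section 4 is people of 18 or more "years of age with LGMD2I", and the criteria in 4.2 and 4.3 set no upper age limit. Age at consent is on the CRF (SAP 6.2.1). No other section of either document adds an age adjustment to BMD.

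**The concern.** A normalised score is printed beside raw BMD so that a subject can be compared with peers. A mean and SD that depend on gender alone do not give that comparison when subjects span adult life and BMD varies with age. A younger and an older subject with equally ordinary bones for their ages get different scores. Readers are likely to take the z-score label as meaning that age has been handled.

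Bone density is part of the safety endpoint (Protocol 2.2.2, SAP 3.4). Protocol 3.2 lists osteopenia and fracture risk among the adverse events associated with deflazacort, and Protocol 1.3 relies on bone-health monitoring that includes DEXA. SAP section 9 moves laboratory, vital-sign, ECG and ophthalmology data to listings, but bone density stays in summary tables.

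With 11 subjects enrolled, and DEXA not available for all of them, one or two subjects at an age extreme can move a mean level. The set of contributors can also change by visit, because only some subjects were eligible to continue beyond Week 26 (Protocol 3.4). A different age mix at Week 52 could then shift the mean normalised level with no change in anyone's bone.

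**Working it through.** The plan states no BMD reference mean, SD or expected score, so there is no figure of its own to reproduce. The check is algebra on the SAP formula, followed by an illustration of size.

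**Inputs from the documents.** Standardisation is by gender only, for both mean and SD (SAP 6.12.7). Eligibility is 18 and over with no upper limit (Protocol 4.2, 4.3). Eleven subjects were enrolled (SAP section 1).

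**Assumed inputs, not in the documents.** Within a gender, BMD falls linearly with age by b = 0.1 to 0.4 within-age SD per decade. The reference sample is pooled over ages, with mean age 45 and age SD A = 1.5 to 2.0 decades.

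**Level.** Write BMD = m(age) + s·e, where s is the within-age SD and e is the true age-and-gender-matched z. With gender mean M and SD S, the SAP score is

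(BMD − M)/S = [m(age) − M]/S + (s/S)·e.

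The first term depends on age alone. For a reference pooled over ages, S = s·√(1 + (bA)²). A subject exactly average for age has e = 0 and would score 0 under age-matched standardisation. Under the SAP formula that subject scores +2b/√(1 + (bA)²) at age 25 and the negative of that at age 65. The gap is 4b/√(1 + (bA)²).

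| b | A (decades) | S/s | Score at 25 / 65 | Gap | Share of change kept (s/S) |
|---|---|---|---|---|---|
| 0.1 | 1.5 | 1.011 | +0.20 / −0.20 | 0.40 | 0.989 |
| 0.1 | 2.0 | 1.020 | +0.20 / −0.20 | 0.39 | 0.981 |
| 0.2 | 1.5 | 1.044 | +0.38 / −0.38 | 0.77 | 0.958 |
| 0.2 | 2.0 | 1.077 | +0.37 / −0.37 | 0.74 | 0.928 |
| 0.3 | 1.5 | 1.097 | +0.55 / −0.55 | 1.09 | 0.912 |
| 0.3 | 2.0 | 1.166 | +0.51 / −0.51 | 1.03 | 0.857 |
| 0.4 | 1.5 | 1.166 | +0.69 / −0.69 | 1.37 | 0.857 |
| 0.4 | 2.0 | 1.281 | +0.62 / −0.62 | 1.25 | 0.781 |

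The age-only gap therefore runs from 0.39 to 1.37 score units. For a whole cohort whose mean age is 10 years from the reference mean, the mean score moves by b/√(1 + (2b)²), or 0.10 to 0.31 for A = 2.0.

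**Change from baseline.** The reference mean cancels:

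(BMD_visit − M)/S − (BMD_baseline − M)/S = (BMD_visit − BMD_baseline)/S.

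Numerical check with invented values: a fall from 0.90 to 0.88 with S = 0.15 gives −0.133 whether M is 0.8, 1.0 or 1.2. Only the divisor matters. If the between-age SD is 0.3 to 0.5 of the within-age SD (assumption), S/s = √1.09 = 1.044 to √1.25 = 1.118. The change then shrinks by 1 − 1/1.044 = 4% to 1 − 1/1.118 = 11%. Across the wider grid in the table the shrinkage is 1% to 22%. Ordinary ageing over 26 weeks (0.05 decade) contributes at most about −0.05 × 0.4/1.166 = −0.02.

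**The case against.** A reader might infer that the method understates or conceals bone loss on treatment. The documents do not support that. In change from baseline the reference mean drops out, leaving one fixed divisor per gender. Within a gender, a fixed divisor cannot alter the sign of a change or its size relative to its own variability. The same section also summarises raw BMD and raw change by visit, and these need no reference.

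A reader might also infer that the reference is the whole survey sample pooled over all ages. SAP 6.12.7 does not say so; it gives no reference ages. If young adults were used, the score would resemble a T-score and the inflated-SD argument would largely fall away. The score would still not be adjusted for age: with S close to s, the gap between ages 25 and 65 would be about 4b, or 0.4 to 1.6. The SAP cites a source on T-scores and z-scores, but that source is not part of the documents and cannot settle which reference is meant.

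Further points stand against giving this much weight. The direction and size of the age effect rest on an assumed gradient. No hypothesis is tested (Protocol 9.1). No eligibility, dosing or stopping rule in the documents uses the normalised score. Protocol 9.5.7.3 does not ask for it, so it is a supplementary scale, and the SAP states openly that the adjustment is by gender. Age cells also have a price: smaller reference groups, noisier reference SDs and steps at band boundaries.

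These points limit the reach of the concern. They do not remove the age term from the score levels.

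**Conclusion.** The point holds for the levels of the normalised score and for its label. SAP 6.12.7 standardises by gender alone, leaves the reference ages unstated and calls the result a z-score, in a population open to every adult age.

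Under the assumed gradients and reference age spread, age alone separates two age-average subjects of 25 and 65 by about 0.4 to 1.4 score units. For change from baseline only the unit is affected, by about 4% to 11% under the stated assumption of an age-pooled reference. Raw change is reported alongside, so the assessment of bone loss on treatment is largely protected.

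The algebra follows from the SAP's formula whenever BMD varies with age; every magnitude rests on figures that the documents do not contain. Severity is minor: this is a descriptive safety summary in at most 11 subjects, and it can be improved cheaply.

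**What to change.** In SAP 6.12.7:

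- Compute the reference mean and SD by gender and age band from the same reference data, with bands broad enough to give stable cells, and standardise each subject to the matching cell.
- Fix each subject's cell at the pre-deflazacort baseline (SAP 6.2.3), so that a birthday between visits cannot alter the change score. For subjects first randomised to placebo, this is the baseline before open-label deflazacort.
- State the age range of the reference sample for each skeletal site.
- If age cells are not feasible for a skeletal site, label that score *gender-standardised, not age-adjusted* and list each subject's age beside it.

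Keep the raw BMD and raw change summaries as planned. The cost should be a small amount of programming on a dataset the SAP already uses, provided that dataset carries usable ages and adequate cell counts, which cannot be checked from the documents. The statistical downside is smaller reference cells, which broad bands limit. No new subject data are needed, because age is already on the CRF.

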7 INTERIM ANALYSIS

No interim analyses are planned for this study.

8 DATA SAFETY MONITORING BOARD ANALYSIS

No data safety monitoring board (DSMB) analyses are planned.

QMD Ref: Worldwide-TMP-ST-005-7.0 Effective: 12Aug2019	Governing QMD: Worldwide-SOP-ST-001
Confidentiality Statement	
This document is the property of Worldwide Clinical Trials Inc. and may not be duplicated, copied, altered or removed from company without prior approval from Worldwide Quality Assurance or in compliance with Worldwide Standard Operating Procedures.	

Worldwide Clinical Trials Controlled Quality Management Document		
 WORLDWIDE CLINICAL TRIALS	Sponsor:	PTC Therapeutics, Inc
	Protocol Number:	PTCEMF-GD-004
STATISTICAL ANALYSIS PLAN		

9 CHANGES TO PLANNED PROTOCOL ANALYSIS

Due to the early termination of the study (decision made 23rd July 2020), only 11 subjects were enrolled in the study with limited information. Medical History, Concomitant medications, Exploratory Efficacy Endpoints (except fat fraction), Laboratory results, Vital Signs, ECG, Physical Examination and Ophthalmology examination information will be presented only in listings instead of summary tables. In addition, Dixon MRI and T2 MRI endpoints is not collected and will not be summarized or listed.

11 APPENDIX 1: DATA HANDLING

Duration / Study Day / Time

Study day will be calculated as the number of days from first dose of deflazacort.

- date of event – date of first dose of deflazacort + 1, for events on or after first dose
- date of event – date of first dose of deflazacort, for events before first dose

Conventions for Missing and Partial Dates

All rules explained below for partial / missing dates will be followed unless contradicted by any other data recorded on the electronic Case Report Form (eCRF).

All dates presented in the individual subject listings will be as recorded on the eCRF (i.e., not completed as per the below rules).

Missing / Partial Start / Stop Date of Adverse Events (AE) and Concomitant Medications

Generally, if the adverse event (AE) or medication stop date is completely missing, no imputation will be done. AE will be considered as treatment emergent adverse event (TEAE) and medication will be considered as concomitant.

Missing and partial start and stop dates will be imputed for analysis purposes as follows.

Partial or missing start date will be imputed as follows:

- Missing day only
 - If the month and year are the same as the year and month of the first deflazacort date, then the first dosing date will be assigned to the missing field.
 - If the partial date (year and month) is prior to the first deflazacort date (year and month), then the last day of the month will be assigned to the missing field.
 - If the partial date (year and months) is after the first deflazacort date (year and month), then the first day of the month will be assigned to the missing field.
- Missing month only
 - The day will be treated as missing and both month and day will be imputed according to the imputations rules for missing day and month.
- Missing day and month

QMD Ref: Worldwide-TMP-ST-005-7.0 Effective: 12Aug2019	Governing QMD: Worldwide-SOP-ST-001
Confidentiality Statement	
This document is the property of Worldwide Clinical Trials Inc. and may not be duplicated, copied, altered or removed from company without prior approval from Worldwide Quality Assurance or in compliance with Worldwide Standard Operating Procedures.	

Worldwide Clinical Trials Controlled Quality Management Document		
 WORLDWIDE CLINICAL TRIALS	Sponsor:	PTC Therapeutics, Inc
	Protocol Number:	PTCEMF-GD-004
STATISTICAL ANALYSIS PLAN		

- If the year is the same as the year of the first dosing date, then the first dosing date will be assigned to the missing field.
- If the year is prior to the year of the first dosing date, then December 31 will be assigned to the missing field.
- If the year is after the year of the first dosing date, then January 1st will be assigned to the missing field.
- Missing year
 - No Imputation will be done.
 - The AE will be considered as TEAE if the end date is missing or after the first dosing date.
 - The medication will be considered as both prior and concomitant if the end date is missing or after the first dosing date.

If the stop date is non-missing and the imputed start date is after the stop date, the start date will be imputed by stop date.

Partial or missing stop date will be imputed as follows:

- Missing day only
 - If the month and year are the same as the year and month of the last deflazacort date, then the last dosing date will be assigned to the missing field.
 - If the partial date (year and month) is prior to the last deflazacort date (year and month), then the last day of the month will be assigned to the missing field.
 - If the partial date (year and months) is after the last deflazacort date (year and month), then the first day of the month will be assigned to the missing field.
- Missing month only
 - The day will be treated as missing and both month and day will be imputed according to the imputations rules for missing day and month.
- Missing day and month
 - If the year is the same as the year of the last dosing date, then the last dosing date will be assigned to the missing field.
 - If the year is prior to the year of the last dosing date, then December 31 will be assigned to the missing field.

QMD Ref: Worldwide-TMP-ST-005-7.0 Effective: 12Aug2019	Governing QMD: Worldwide-SOP-ST-001
Confidentiality Statement	
This document is the property of Worldwide Clinical Trials Inc. and may not be duplicated, copied, altered or removed from company without prior approval from Worldwide Quality Assurance or in compliance with Worldwide Standard Operating Procedures.	

Worldwide Clinical Trials Controlled Quality Management Document		
 WORLDWIDE CLINICAL TRIALS	Sponsor:	PTC Therapeutics, Inc
	Protocol Number:	PTCEMF-GD-004
STATISTICAL ANALYSIS PLAN		

- If the year is after the year of the last dosing date, then January 1st will be assigned to the missing field.
- Missing year
 - No Imputation will be done.
 - If both start and stop date of an AE are missing, the AE will be considered as TEAE
 - If both start and stop date of a medication are missing, the medication will be considered as both prior and concomitant medication.

If the start date is non-missing and the imputed stop date is before the start date, the stop date will be imputed by start date.

Inexact Values

In the case where a variable is recorded as “> x”, “≥ x”, “< x” or “≤ x”, a value of x will be taken for analysis purposes.

QMD Ref: Worldwide-TMP-ST-005-7.0 Effective: 12Aug2019	Governing QMD: Worldwide-SOP-ST-001
Confidentiality Statement	
This document is the property of Worldwide Clinical Trials Inc. and may not be duplicated, copied, altered or removed from company without prior approval from Worldwide Quality Assurance or in compliance with Worldwide Standard Operating Procedures.	

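### Read literally, SAP Appendix 1 makes any AE with a completely missing stop date a TEAE whatever its start date, which conflicts with the definition in SAP 6.12.1

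*SAP*

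**What the plan says.** SAP 6.12.1 sets up three classes, all placed by timing against deflazacort:

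- "TEAE is defined as the AE occurring or worsening on or after the first deflazacort dose", with the window closing 30 days after the last dose.
- "Pre-treatment AE is defined as the AE occurring prior to the start of the deflazacort treatment".
- "Post-treatment AE is defined as the AE occurring after 30 days of the last deflazacort dose".

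The stop date appears in none of them.

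SAP Appendix 1 then handles an absent stop date. It says: "Generally, if the adverse event (AE) or medication stop date is completely missing, no imputation will be done". The next sentence gives the consequence: "AE will be considered as treatment emergent adverse event (TEAE) and medication will be considered as concomitant". It sets no start-date condition.

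Three other parts of Appendix 1 bear on how far that sentence reaches:

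- The missing-date rules apply "unless contradicted by any other data recorded on the electronic Case Report Form (eCRF").
- For a missing start year: "The AE will be considered as TEAE if the end date is missing or after the first dosing date".
- For two missing dates: "If both start and stop date of an AE are missing, the AE will be considered as TEAE".

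**The concern.** One trigger serves both medications and AEs. It fits medications, because SAP 6.8 defines concomitant use as use during the deflazacort period, so an open stop date bears directly on the class. It fits AEs less well, because emergence depends on when the event began or worsened.

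Two programmers could each follow the SAP and put the same event in different classes. For pre-dose events, the literal reading can only add TEAEs. This matters somewhat more than usual here. SAP Section 9 moves laboratory, vital sign, ECG, physical examination and ophthalmology results to listings, so the TEAE tables are among the few safety summaries left, with the bone assessments in 6.12.7.

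**Working it through.** The plan gives no figure to reproduce. The check sets the two rules side by side and then sizes the effect of one event.

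**Inputs**

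- TEAE window: first deflazacort dose to last dose + 30 days (SAP 6.12.1).
- Start-date imputation and the missing-stop-date sentence (SAP Appendix 1).
- AE reporting starts at consent and runs for at least 30 days after the last dose (Protocol 8.4.8).
- Screening falls within 42 days of Visit 1 (Protocol Schedule of Events, footnote 1).
- Events after the reporting period are recorded only if judged possibly related (Protocol 8.4.5).
- 11 subjects enrolled (SAP Section 9). The number dosed is not given.

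**Step 1: assumed dates.** Take a subject never on placebo, with first dose 10 Mar 2020 and last dose 8 Sep 2020. The 42-day window opens 10 Mar − 42 days = 28 Jan 2020. The TEAE window closes 8 Sep + 30 days = 8 Oct 2020. The AE stop date is completely missing. Unless stated, the AE did not worsen.

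| Recorded start | Start used | SAP 6.12.1 | Literal Appendix 1 | Agree? |
|---|---|---|---|---|
| 10 Feb 2020 | day −29 | pre-treatment | TEAE | no |
| Feb 2020, day missing | 29 Feb (day −10) | pre-treatment | TEAE | no |
| 10 Feb 2020, worsening recorded on treatment | day −29 | TEAE | TEAE | yes |
| Mar 2020, day missing | 10 Mar (first dose) | TEAE | TEAE | yes |
| 1 May 2020 | 1 May | TEAE | TEAE | yes |
| 2020, day and month missing | 10 Mar (first dose) | TEAE | TEAE | yes |
| Year missing | none imputed | TEAE by the missing-year rule | TEAE | yes |
| 20 Oct 2020 | 20 Oct | post-treatment | TEAE | no |
| Nov 2020, day missing | 1 Nov | post-treatment | TEAE | no |

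Study days before dosing use the Appendix 1 formula, event date minus first-dose date: 10 Feb − 10 Mar = −29, and 29 Feb − 10 Mar = −10.

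The rules part company only when the start date places onset before the first dose without worsening, or more than 30 days after the last dose. The rows are constructed cases, so the share that disagrees is not a frequency.

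**Step 2: how exposed is each group?** The pre-dose group can arise, because AEs are collected from consent, but the interval is about six weeks at most. The late group should be small, because collection need not run past 30 days and later events enter only if judged possibly related.

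**Step 3: size of one event.** If one subject has such an AE and no other TEAE in the row, incidence shifts by 1/n, where n is the number dosed with deflazacort.

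- n = 11 (all enrolled were dosed): 1/11 = 9.1 points.
- Assumed n = 10, 9, 8: 1/10 = 10.0, 1/9 = 11.1 and 1/8 = 12.5 points.

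**The case against.** The best defence is that Appendix 1, read as a whole, already has the narrower meaning. The rule opens with *Generally*, and the eCRF clause lets recorded data override it. The missing-end-date branch of the missing-year rule, and the both-dates rule, would be redundant for AEs if any missing stop date were enough. Start-date imputation also keeps earlier partial dates before the first dose. These are fair signals of intent, and they reduce the point. They do not remove it: none says that a recorded pre-dose start overrides the rule. A pre-dose start alone does not contradict TEAE status either, since worsening also counts.

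A second argument stands in part. A reader might infer that a missing stop date says nothing about emergence. The documents do not support that. A stop date before the first dose would rule out worsening on treatment, whereas a missing one leaves it open. Protocol 8.4.5 lists onset and resolution dates but no worsening date, and 8.4.7 asks only for the highest grade per episode. Where worsening cannot be excluded, a TEAE default is a defensible cautious convention, and any rewording must keep it.

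Third, Protocol 8.4.1 keeps pre-existing conditions out of AE reporting unless they worsen or become more frequent. Whether that covers conditions arising after consent is arguable. If it does, fewer events are exposed.

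A reader might also infer that placebo-period AEs would enter the TEAE tables. SAP Sections 6, 6.3 and 6.12 send them to listings only, and those specific rules should prevail over a general one.

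**Conclusion.** The point holds as a minor inconsistency in a stated rule. Taken literally, the Appendix 1 sentence over-counts TEAEs for events with recorded pre-dose onset, no worsening and no stop date, and misplaces a probably small number of late-onset events. Elsewhere, it gives the same class as 6.12.1 and the other Appendix 1 rules.

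The documents do not show that any reported TEAE count is inflated. The number of affected events is unknown and may be zero. They also do not show whether the eCRF separates an ongoing event from one whose stop date is missing. The shift of 9.1 points assumes one affected subject, no other TEAE for that subject in the row, and all 11 enrolled dosed. The study is single-arm and descriptive with no hypothesis test, and the planned AE listings show dates as recorded, so a misplaced event could be traced. The summary table would still carry it.

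**What to change.** Replace the AE part of the sentence in Appendix 1 with:

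> A completely missing AE stop date will not be imputed and does not by itself make the AE a TEAE. The AE will be classified under Section 6.12.1 by its observed or imputed start date and any recorded worsening. It will be a TEAE by default when the available eCRF data cannot exclude onset or worsening between the first deflazacort dose and 30 days after the last dose. An AE with onset before the first dose and no evidence of worsening in the eCRF (no later AE record or increase in grade) is pre-treatment. If the eCRF cannot show whether it worsened, the TEAE default stays and the event is flagged in the listing.

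Keep the medication rule, the missing-year and both-dates-missing rules, and the listings-only handling of placebo-period AEs.

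The cost is part of one sentence and a listing flag, with no new data or design change. The small downside is that a few flagged events may still be over-counted, but they would be visible.
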